55 confounding effect of different body fast distribution at baseline. Study subjects will be
56 randomized in two groups of 20 patients to receive additional liraglutide or to remain on
57 current treatment/ placebo prior to cardiac surgery. EAT samples will be collected during
58 cardiac surgery and processed for analysis of mRNA and protein expression of EAT
59 inflammatory genes such as Tumor Necrosis Factor-alpha (TNF- α) and Interleukin 6 (IL-
60 6), and GLP-1R.

62 Table of Contents

63 Background

64 **EAT Anatomy and Physiology:** EAT is the visceral fat depot of the heart.¹⁻³ EAT and
 65 intra-abdominal fat have the same embryogenesis and both evolve
 66 from brown fat (BAT). EAT is supplied by branches of the
 67 coronary arteries and no muscle fascia separates the fat depot and
 68 the myocardium (*as depicted in the microscopic figure of human*
 69 *EAT*). Hence, as the two tissues share the same microcirculation,
 70 a direct cross-talk between the EAT and the myocardium has been
 71 highly suggested. Under physiological conditions EAT could serve as a buffer, absorbing
 72 fatty acids and protecting the heart against high fatty acids levels, as a lipid storage and
 73 local energy source channelling fatty acids to the myocardium and as BAT to defend the
 74 myocardium against hypothermia. Under pathological conditions EAT releases factors that
 75 promote harmful coronary artery and myocardial changes. EAT is an extremely active
 76 organ that produces both pro-inflammatory, such as TNF- α , IL-6, and anti-inflammatory
 77 adipokines.¹⁻³ Given its anatomical proximity to the heart, EAT may interact locally and
 78 modulate the myocardium and coronary arteries through paracrine or vasocrine secretion
 79 of bioactive molecules. EAT transcriptome is also unique when compared to subcutaneous
 80 fat. EAT is a highly inflammatory tissue enriched with genes involved in inflammation,
 81 endothelial function, coagulation, immune signalling and apoptosis.⁴

82 **EAT and Coronary Artery Disease:** EAT plays a significant role in the development and
 83 progression of CAD.⁵⁻⁶ EAT could alter the coronary arteries via multiple pathways
 84 including macrophage activation, inflammatory response, oxidative stress and plaque
 85 destabilization. Epicardial adipocytes display an intrinsic pro inflammatory and
 86 atherogenic profile. A dense inflammatory infiltrate, mainly represented by macrophages,

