234 Liraglutide. The randomized, double-blind, placebo-controlled study design will allow for
235 an independent and unbiased effect of Liraglutide on study results. In addition, actions to
236 equalize weight loss and maintain similar glucose control between study arms will rule out
237 the confounding effects of these factors on the study outcomes.

238 **Specific Objectives**

239 **Primary Objective:**

240 • to test the hypothesis that liraglutide can reduce the pro-inflammatory
241 transcriptome profile of EAT of subjects with T2DM and CAD.

242 **Secondary Objectives:**

243 • to assess the hypothesis that liraglutide will reduce the ultrasound measured EAT
244 thickness in subjects with T2DM and CAD.
245 • to evaluate the hypothesis that liraglutide can produce more anti-inflammatory
246 effects in the EAT as compared to SAT of subjects with T2DM and CAD.
247 • to test the hypothesis that EAT mRNA and protein expression of GLP-1R will be
248 greater in subjects receiving liraglutide as compared to those continuing their
249 standard therapy

250

251 **Research Design and Methods**

252 **Study Hypotheses**

253 **Hypothesis for Primary Objective:** We hypothesize that EAT inflammatory gene mRNA
254 and protein expression will be lower in subjects receiving additional therapy with
255 liraglutide as compared to those who will continue with their current treatment.

256 **Hypothesis for Second Objectives:** based on our biomolecular and clinical preliminary
257 data, we hypothesize that a) EAT thickness will respond and decrease more on liraglutide
258 than on standard therapy, b) inflammatory genes and protein expression will be different
259 in EAT vs SAT c) EAT GLP-1R expression will be greater in patients on liraglutide vs
260 those on standard therapy.

261

262 **Endpoints**

263 **Primary Endpoint:**

264 • Change from baseline in EAT inflammation (measured as mRNA and protein
265 expression of TNF- α and IL-6) within a minimum of 3 and up to 12 weeks of treatment

266 **Secondary Endpoints:** Change from baseline within a minimum of 3 and up to 12 weeks of
267 treatment for the following parameters:

- 268 • Ultrasound measured EAT thickness
- 269 • SAT inflammation (measured as mRNA and protein expression of TNF- α and IL-6)
- 270 • EAT GLP-1R (measured as mRNA and protein expression of GLP-1R)

271 **Study Type**

272 This is an Investigator Sponsored Study (ISS).

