273 This will be a 12-week randomized, double-blind, placebo-controlled interventional study
274 in 40 patients with T2DM and CAD with an acceptable glycemic control on their current
275 diabetes regimen who require elective coronary artery bypass grafting (CABG) regardless
276 of their participation in the study.

277 A minimum time frame of 3-week treatment will be considered to detect significant
278 changes in the study endpoints. If not all subjects would be able to complete the 12
279 weeks, study outcomes will be evaluated at the 3 week time point.

280

281 **Study Design** Study subjects will be randomized in two groups of 20 patients to receive
282 additional liraglutide, (L-group) or to remain on current treatment or placebo (D-group).

- 283 • L-group will be started on liraglutide. Liraglutide will be started and administered
284 for 12 weeks prior to CABG with a starting dose of 0.6 mg (after a least one week)
285 and subsequent increments to 1.2 mg (after a least one week) and to 1.8 mg (after
286 at least a week on 1.2 mg). The dose of 1.8 mg daily will be maintained until the
287 end of the 12-week study. Other and current diabetes treatment will be continued.
288 In those study participants who may be impacted by CABG scheduling and
289 COVID-19, and cannot complete the 12-week treatment, we will consider a
290 minimum time frame of 3 weeks to detect significant changes in the study primary
291 endpoints.
- 292 • D-group: placebo will be administered in addition to current treatment prior to the
293 CABG with a starting dose of 0.6 mg (after a least one week) and subsequent
294 increments to 1.2 mg (after a least one week) and to 1.8 mg (after at least a week
295 on 1.2 mg). Patients will be started on a supervised diet to achieve approximately
296 5% of weight loss between 3 and 12 weeks. In those study participants who may be
297 impacted by CABG scheduling and COVID-19, and cannot complete the 12-week
298 treatment, we will consider a minimum time frame of 3 weeks to detect significant
299 changes in the study primary endpoints.

300

301 Ultrasonographic measurement of EAT thickness will be performed at baseline and
302 after 12 weeks in all patients, regardless of the study arm.

303 All groups will receive lifestyle and diabetes education, and supervised diet as
304 part of the standard care, to insure similar glycemic control between arms and
305 weight loss. Study patient will be also required to check and log their finger stick

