380 methods (as required by local law or practice)

381

382 **Investinational drug**

383 Liraglutide [rDNA origin] injection, solution for subcutaneous use. Liraglutide will be
384 prescribed according to the same, current indications of the marketed Victoza.

385

386 **Withdrawal Criteria**

387 1. The subject may withdraw at will at any time.
388 2. The subject may be withdrawn from the trial at the discretion of the investigator due to
389 a safety concern or if judged non-compliant with trial procedures or included in
390 contravention to the inclusion and/or exclusion criteria.
391 3. Subject diagnosed with acute pancreatitis by clinical and/or radiographic criteria.
392 4. Pregnancy, positive pregnancy test prior to the enrollment or intention to become
393 pregnant.
394 5.
395 6. Subjects who will not tolerate liraglutide dose increase to 1.2 or 1.8 mg will remain in
396 the study at the highest tolerated dose

397 **Subject Replacement**

398 There will be no replacement of subjects in this trial.

399

400 **Rationale for Study Population**

401 We anticipate that approximately 400 patients will be screened in a 2-year period. We will
402 recruit patients with T2DM and clinically and angiographically stable CAD who will
403 undergo CABG surgery, as part of their standard medical care. Cardiac surgery will be
404 elective procedure in hemodynamically stable patients taking their standard cardiac
405 treatments and under the care of the cardiologist.

406

407 **Recruitment strategy:** Participants will be recruited among the outpatient population who
408 routinely refer to the Division of Cardiothoracic Surgery ([name] and collaborators),
409 Division of Cardiology ([name]) and Division of Endocrinology, Diabetes and
410 Metabolism outpatient clinics ([name]), at University of Miami.

411 **Visit Procedures**

412 **Study Timetable:** This study will consist of two clinical visits prior the cardiac surgery
413 and adipose tissue collection during the surgical intervention. Consecutive subjects with
414 T2DM and CAD who are candidate for elective cardiac surgery regardless of their
415 participation in the study will be selected, informed and consented. Patients suitable to
416 wait 12 weeks for cardiac surgery will be identified by the cardiology team and accordingly
417 scheduled, as part of the standard care. Anthropometrics, blood draw for laboratory
418 measures and echocardiographic measurements of EAT thickness will be performed at

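### The primary endpoint and two secondary endpoints are defined as change from baseline in tissue expression, but fat is sampled only once, at surgery after treatment, so three of the four endpoints cannot be computed as defined

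*Combined protocol and SAP*

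**What the plan says.** **Endpoints.** The primary endpoint is "Change from baseline in EAT inflammation (measured as mRNA and protein" expression of TNF-α and IL-6, over 3 to 12 weeks of treatment. One stem covers all three secondary endpoints: "Change from baseline within a minimum of 3 and up to 12 weeks of" treatment. They are ultrasound EAT thickness, SAT inflammation and EAT GLP-1R.

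**Sampling.** The Abstract states that "EAT samples will be collected during" cardiac surgery. The Study Timetable provides for two clinic visits before surgery "and adipose tissue collection during the surgical intervention". Under Adipose tissue collection, SAT is taken from the thoracic wound and EAT from near the right coronary artery. The risk section calls the collection intra-operative, and the Power Analysis also places it at surgery. The baseline procedures in the Study Timetable are anthropometrics, blood and echocardiography. Study Design says: "Ultrasonographic measurement of EAT thickness will be performed at baseline and" again after 12 weeks.

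**Hypotheses.** The primary hypothesis is that EAT inflammatory gene mRNA "and protein expression will be lower in subjects receiving additional therapy with" liraglutide than in those continuing current treatment. One secondary objective is that liraglutide has greater anti-inflammatory "effects in the EAT as compared to SAT of subjects with T2DM and CAD". The matching hypothesis reads "than on standard therapy, b) inflammatory genes and protein expression will be different" in EAT versus SAT.

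**The concern.** A change from baseline needs two measurements per patient, and the tissue endpoints have one. As written, the primary endpoint names a quantity that no patient's data can supply. The report must then either depart from its own primary endpoint or present a between-arm difference at surgery as if expression had fallen within patients. One post-treatment sample can support a statement that expression was lower than on placebo at surgery. It cannot support a statement that expression fell from baseline. Nor can chance imbalance in pre-treatment expression, with 20 patients per arm, be checked or adjusted for.

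The EAT-versus-SAT mismatch is separate and weighs less. A plain difference between the two fats could be reported as meeting the objective although it says nothing about liraglutide.

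**Working it through.** The main point rests on comparing the endpoint list with the sampling schedule. The arithmetic only shows what does and does not follow.

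**1. Endpoints against samples**

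| Endpoint | Baseline | After treatment | Change computable? |
|---|---|---|---|
| EAT TNF-α and IL-6 (primary) | none | at surgery | no |
| EAT thickness (echo) | yes | yes | yes |
| SAT TNF-α and IL-6 | none | at surgery | no |
| EAT GLP-1R | none | at surgery | no |

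Three of four cannot be computed as defined. The provision for outcomes at 3 weeks concerns patients who cannot complete 12 weeks of treatment. It adds no baseline sample.

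**2. What was intended**

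- The primary hypothesis, hypothesis (c) and the GLP-1R objective all compare liraglutide with the other arm.
- The Power Analysis takes a between-arm difference in expression, with a 42% coefficient of variation (CV) of expression from 5 patients. It gives no SD of change. The text on 3-week treatment also compares liraglutide with placebo.
- The test paragraph compares mRNA and protein between liraglutide and placebo, and uses before-and-after wording only for ultrasound thickness. A two-sample test could also be run on change scores, so the choice of test alone would not settle the matter. The contrast with echo does point to levels at surgery.

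**3. The plan's power figure**

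Inputs (Power Analysis): 33% difference, CV 42%, 20 per arm, two-sided α 0.05, power set at 90%. On the log scale:

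- difference = |ln(0.67)| = 0.400
- SD = √ln(1 + 0.42²) = 0.403
- standardised difference = 0.400 / 0.403 = 0.994
- power at 20 per arm = 88.1% (normal approximation), close to the stated 90%

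On the raw scale, 0.33 / 0.42 = 0.786 gives 70.0%. Both calculations address expression at one time point compared between arms, so redefining the endpoint leaves them as they are. A change score would need a within-patient correlation ρ over time, which the documents do not give. Assuming ρ = 0.3, 0.5 or 0.7, the SD is multiplied by √(2(1 − ρ)) and log-scale power would be 75.7%, 88.1% or 98.2%.

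**4. EAT versus SAT**

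Hypothesis (b) can be true with no drug effect. The Power Analysis already reports IL-6 and TNF-α as higher in EAT than in SAT in preliminary data, and says that no data exist on liraglutide and EAT inflammation. The objective needs the treatment effect in EAT set against that in SAT, and no planned analysis does this.

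For the precision of that contrast, assume SAT shares the 42% CV and let ρ be the within-patient EAT–SAT correlation (not given, so a range is shown):

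- SD of log(EAT) − log(SAT) = 0.403 × √(2(1 − ρ)) = 0.570, 0.403, 0.255 at ρ = 0, 0.5, 0.8
- detectable standardised difference, two-sample t-test, 20 per arm, 80% power: 0.909
- detectable ratio of treatment ratios (EAT/SAT) = exp(−0.909 × SD) = 0.60, 0.69, 0.79

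These are effect sizes at a fixed 80% power. A ratio of 0.60 is not an effect 40% larger in EAT. If the SAT treatment ratio were 0.90 (a 10% reduction), the EAT ratio would be 0.60 × 0.90 = 0.54 (a 46% reduction).

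**The case against.** The strongest reply is that this is only a wording slip. The hypotheses, GLP-1R objective, power text and test paragraph all point to a between-arm comparison, and no sample, procedure or patient number has to change. Most of that stands. But the slip is in the formal definition of the primary endpoint, which conflicts with the plan's own hypothesis and sampling. It also decides whether the trial may claim a reduction or only a difference.

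A reader might infer that the trial cannot test its primary hypothesis, or that the sample size must be redone. The documents do not support either reading, because the comparison at surgery is feasible and is the one that was powered. Feasible is as far as this point goes. Patients who withdraw before surgery give no tissue and are not replaced, and Study Design describes the control arm as current treatment or placebo. Whether the 90% power figure is fully met is another question.

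Hypothesis (b) can also be read as shorthand for the objective it sits under. That is fair and makes the mismatch minor, but the analysis that would answer the objective is still not stated.

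**Conclusion.** The point holds. Three of the four endpoints, including the primary, cannot be computed as defined for any patient, because EAT and SAT have no pre-treatment sample. This rests on the endpoint wording and sampling schedule and needs no numerical assumption. It must be fixed because it sits in the primary endpoint and limits what may be claimed. The stated N of 40 and the power calculation are unaffected.

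The EAT-versus-SAT mismatch holds with lesser weight. Its precision figures depend on two assumptions that the documents do not supply: a SAT CV of 42% and the EAT–SAT correlation.

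**What to change.** 1. Redefine the three tissue endpoints as expression in the sample taken at surgery, compared between arms. Name one form of primary estimate: the liraglutide/placebo ratio of geometric means on log-transformed values, with Mann-Whitney as supporting analysis. At present, log transformation and the switch to Mann-Whitney both depend on normality, which leaves the estimate open.
2. Reconcile this with the statements under Study Type and Study Timetable that outcomes are evaluated or collected at 3 weeks when 12 weeks cannot be completed. Tissue exists only at surgery, and the rationale for the minimum time line says that the surgery date sets the length of treatment.
3. Keep change from baseline for echo EAT thickness only.
4. For the EAT-versus-SAT objective, compute log(EAT) minus log(SAT) within each patient and compare it between arms, labelled as secondary with no stated power. If precision is quoted, give the detectable ratios of treatment ratios with their assumptions.
5. Word tissue conclusions as lower (GLP-1R: higher) than placebo at surgery, not as a within-patient reduction.

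The cost is a protocol amendment with IRB review, before unblinding if that is still possible. The Study Schedule gives the last visit as 10/31/2023 and the final report as 12/2023. If unblinding has passed, disclose the change in the report as a correction. If the registry entry carries the same wording, align it. No new patient, sample or procedure is needed. The downside is giving up a within-patient reduction claim that the design cannot support.

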307 blood glucose twice daily (fasting before breakfast and at bedtime) and report the
308 readings to the study coordinator on a bi-weekly base.
309

310 **Rationale for study Design**

311 The randomized, double-blind, placebo-controlled study design will allow for an
312 independent and unbiased effect of liraglutide on study results.
313

314

315 **Rationale for minimum study time line of 3 weeks.**

316 The pre-operative clinic schedule may not always allow to wait the full 12 weeks between
317 the patient's enrollment and the CABG, standard of care procedure. [name] is the only
318 cardiac surgeon at UM performing elective CABGs. Once the patient is randomized and
319 randomly allocated to one of the study arms, the length of the treatment is set by the date
320 of standard of care CABGs. During the current COVID-19 pandemic, the number of
321 elective CABGs has been reduced and we cannot reschedule or delay the surgery
322

323 **Study Population:** Study group will be formed by 40 patients with T2DM and with
324 clinically and angiographically stable CAD who will undergo CABG surgery, as part of
325 their standard medical care. Cardiac surgery will be elective procedure in
326 hemodynamically stable patients taking their standard cardiac treatments and under the
327 care of the cardiologist.

328

329 **Study team and site:** [name] is Professor of Medicine, Division of
330 Endocrinology, Diabetes and Metabolism. [name] pioneered EAT echocardiographic
331 measurement and he is considered the leading expert in the epicardial fat. [name] will
332 lead and supervise liraglutide therapy, EAT measurement, analysis and interpretation of
333 the data. [name], Research Assistant Professor, Dept. Microbiology and Immunology,
334 will lead and supervise adipose tissue analysis. [name] is associate professor
335 of Cardiology and contributes to patient recruitment. [name], professor of
336 cardiothoracic surgery will be the cardiac surgeons for this study. Low calorie diet (LCD)
337 and other nutritional aspects will be managed and supervised by the Division of
338 Endocrinology registered dietitian (RD), as part of the standard care. University of Miami
339 has been the site of several National Health Institute (NIH) studies and many peer-reviewed
340 publications. The Division of Endocrinology Diabetes and Metabolism is fully equipped
341 and trained to visit, follow up and manage patients with diabetes. The Division of

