419 baseline and before cardiac surgery that will be scheduled 12 weeks after study enrollment
420 and treatment. Adipose tissue collection will be collected during the cardiac surgery.
421 Study outcomes will be collected at 3 weeks in both groups in those patient who may not
422 be able to complete the 12- week treatment due to CABG logistics and COVID-19 impact
423 on scheduling

424

425 **Assessments for Efficacy**

426 **Adipose tissue collection:** EAT biopsy samples (average 0.5-1.0 g) will be taken, before
427 heparin administration, near the proximal tract of the right coronary artery. Each tissue
428 sample will be snap frozen in liquid nitrogen and stored at -80 °C until analysis in a freezer.
429 The subcutaneous fat tissue (SAT) will be harvested at the site of the thoracic wound and
430 preserved in the same manner.

431 **Gene expression:** in freshly isolated mature adipocytes (from EAT and SAT), extraction
432 of total RNA, quantification of mRNA, c-DNA generation qRT-PCR will be performed for
433 measuring expression of the inflammatory genes (TNF- α , IL-6) and GLP-1R.

434 **Western Blot:** Total proteins will be extracted from frozen EAT and SAT adipocytes and
435 blotted for TNF- α , IL6, as previously described.

436 In addition to the mRNA expression of GLP1R, we will also measure protein expression
437 of GLP-1R by western blotting. Total cell lysates from the EAT will be obtained as follows.
438 Cells will be resuspended in M-PER (Mammalian Protein Extraction Reagent, Thermo
439 Scientific), incubated on ice for 20 min, sonicated for a few seconds and then centrifuged
440 (14,000 rpm, 15 min, 4°C) to obtain protein lysates which will be stored at -80°C until
441 use. Protein content will be determined by Bradford assay before western blotting runs.
442 Antibodies will be anti-GLP1R Mab 3F52 (Novo Nordisk) and anti-GAPDH (GeneTex)
443 as loading control.

444 **Immunofluorescence**

445 To confirm GLP-1R protein expression, immunofluorescence will be performed on EAT
446 and SAT samples using Mab 3f52 against GLP-1R, as previously described by Pyke et al
447 23-24. This mouse monoclonal antibody has been extensively validated to show its
448 specificity. Due to the relatively low abundance of GLP-1R the immunofluorescence will
449 be performed using a tyramide signal amplification reagent (TSA kit#26 from Molecular
450 probes) according to the manufacturer instructions. In summary, cryosection of the samples

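### The week-3 evaluation rule cannot be applied to tissue taken once at surgery, the follow-up echo has conflicting timings, and the 3-week power claim is wrong as written

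*Combined protocol and SAP*

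**What the plan says.** **Tissue.** The primary endpoint is "Change from baseline in EAT inflammation (measured as mRNA and protein" expression of TNF-α and IL-6), assessed "within a minimum of 3 and up to 12 weeks of treatment" (Endpoints). Visit Procedures has adipose tissue collected during cardiac surgery and describes no earlier sample. The rationale for the 3-week minimum says that once a patient is "randomly allocated to one of the study arms, the length of the treatment is set by the date" of the standard-of-care operation. Scheduling CABG timing allows a wait of 3 to 12 weeks.

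**The 3-week rule.** Study Type says that if not all subjects can complete 12 weeks, "study outcomes will be evaluated at the 3 week time point". The Study Timetable words it differently: outcomes are collected at 3 weeks, in both groups, in those patients who may not complete. The power section adds that gene results from patients who stop short of 12 weeks will be time adjusted, and names no model.

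**Echo.** Study Design puts the second thickness measurement "after 12 weeks in all patients, regardless of the study arm", and the echocardiography section repeats this. The Study Timetable says "This study will consist of two clinical visits prior the cardiac surgery", with measurements at "baseline and before cardiac surgery that will be scheduled 12 weeks after study enrollment". It also selects patients suitable to "wait 12 weeks for cardiac surgery will be identified by the cardiology team and accordingly" scheduled, which does not match the 3-to-12-week wait elsewhere.

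**Power at 3 weeks.** The power analysis equates a 33% difference with about 1.3X fold. It then says the same sample size gives adequate power in patients treated for only 3 weeks, where the expected difference is about 1X fold.

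**The concern.** A rule that names week 3 presupposes an observation at week 3. For tissue there is one only if surgery happens then. Early surgery is expected (the rationale cites clinic scheduling and COVID-19), so the condition that triggers the rule is likely to be met. With 20 patients per arm, the tissue that counts and any correction for treatment length should be settled before results are seen.

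The endpoint wording has a related gap: with no baseline tissue, a change from baseline in expression cannot be calculated for any patient.

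For thickness, a patient operated on before week 12 has more than one stated follow-up time. For power, the 3-week sentence invites a reader to treat an early-surgery subset as adequately powered in its own right.

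**Working it through.** **Timing of tissue.** Take a patient operated on at week 7.
- Study Type: evaluate at week 3. There is no week-3 tissue.
- Study Timetable: collect at week 3, because the patient did not complete 12 weeks. Tissue is taken only at surgery, so this cannot be done either.
- Endpoints: any time from 3 to 12 weeks. The week-7 sample qualifies, but change from baseline needs a second sample that does not exist.

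Both week-3 wordings work for tissue only when surgery falls at week 3.

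**Timing of echo.** For the same patient, Study Design and the echocardiography section give week 12. The Study Timetable puts both visits before surgery and adds 3-week collection for early patients. The 12-week and pre-surgery texts agree only when surgery is at week 12.

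**The 3-week power claim.** There is no figure to reproduce: the plan says adequate and gives no number.

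Inputs, all from the power analysis: two-sided alpha 0.05, CV 42% (from 5 patients), difference 33% or about 1.3X fold, 20 per arm.

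On that fold scale, 1X is a ratio of 1. The effect is ln(1) = 0, and the rejection rate is alpha, 5%, at any sample size.

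A more useful check supposes the full design effect is already present at 3 weeks. The number of 3-week patients is not given, so the 5 and 10 per arm below are assumptions. Log-scale SD = √ln(1 + 0.42²) = 0.403. Standardised effects:
- 33% reduction, log scale: −ln(0.67)/0.403 = 0.994
- 33%, raw scale, constant CV: SDs 0.42 and 0.42 × 0.67 = 0.281, root mean square 0.357; 0.33/0.357 = 0.923
- 33%, raw scale, common SD: 0.33/0.42 = 0.786
- 1.3-fold, log scale: ln(1.3)/0.403 = 0.651
- 2-fold, log scale: ln(2)/0.403 = 1.720

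Two-sample t-test power uses the noncentral t with 2n − 2 degrees of freedom and noncentrality d√(n/2):

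| Reading | 5 per arm | 10 per arm | 20 per arm | n per arm for 80% |
|---|---|---|---|---|
| 33% reduction, log | 28% | 56% | 86% | 17 |
| 33%, constant CV | 25% | 50% | 81% | 20 |
| 33%, common SD | 20% | 38% | 68% | 27 |
| 1.3-fold, log | 15% | 28% | 52% | 39 |
| 2-fold, log | 66% | 95% | >99% | 7 |

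The 20-per-arm column applies only if every randomised patient is a 3-week patient. The 80% benchmark is the level the plan uses for thickness. At the 90% it sets for this endpoint, the first four rows need 23, 26, 36 and 51 per arm.

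On the log scale the 2-fold effect is 0.693/0.400 = 1.7 times the 33% reduction and 0.693/0.262 = 2.6 times the 1.3-fold effect.

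**The case against.** The best defence is that 3 weeks is meant as a minimum. Study Type says so in the sentence before the rule, both arm descriptions repeat it, and Endpoints and Scheduling CABG timing give a 3-to-12-week window. This stands in part. A reader might infer that the analyst is left with no rule and must invent one afterwards. The documents do not support that, because the window is stated in advance. What remains is a sentence that contradicts the window and a time adjustment without a model.

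A reader might also infer that early-surgery patients will have their second echo after the operation. That follows only if two general sentences override the visit schedule, which puts the echo before surgery and provides for early patients. The supportable finding is a contradiction.

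On power, the 5% result shows a wording error, not the trial's power: the authors plainly expected a detectable difference. If 1X fold was meant as a 100% difference, 7 patients per arm give 80%. That reading rescues the claim for a small subset, but it makes the 3-week effect larger than the effect the design assumes overall.

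It is also tempting to say that the appeal to pre-existing data contradicts the statement that no data exist on liraglutide and EAT inflammation. The phrase may refer to other data, such as those behind the CV, and the documents do not settle it. Nor does any section propose restricting the primary analysis to early-surgery patients.

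**Conclusion.** The point holds, and the text should be corrected before analysis.

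- The week-3 rule, in both wordings, cannot be carried out on primary-endpoint tissue from a patient operated on after week 3, and it conflicts with the stated window. Change from baseline cannot be computed for tissue in anyone.
- The echo timings contradict each other for surgery before week 12 and must be reconciled.
- The 3-week power claim is wrong as written. It names no difference, and it credits the whole sample to a subset of unstated size. With the design's own 33% effect, 80% power needs 17 to 39 three-week patients per arm. That is most of the 20 randomised, all of them, or more than there are, depending on the reading.

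The power figures assume that the full effect is present by week 3, that the 42% CV holds, and that the 3-week patients split equally between arms. None of this invalidates a comparison of randomised arms on tissue taken at surgery, and it is not a finding about the 90% power stated for the main comparison.

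**What to change.** - Reconcile Study Type, Study Design, the Study Timetable, the echocardiography section and Scheduling CABG timing to one stated window. Surgery timing stays as set by usual care.
- Define the primary comparison as tissue expression at surgery between assigned arms, in all randomised patients with tissue, whatever week surgery falls in. Say this under Endpoints in place of change from baseline for tissue.
- Take follow-up thickness from the pre-operative echo that the Study Timetable already describes.
- State the form of any time adjustment in advance.
- Delete the 3-week power claim, or restate it with its actual effect, subset size and power.

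The cost is wording changes and the loss of the 3-week power claim as it stands. No patients, visits or samples are added.
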